10.2. Duration of Study Treatment and Exposure to Study Drug

Total number of doses received and total dose (mg) received will be calculated from study drug dispensation and return information. Descriptive summaries for duration of study treatment will include the number of doses received, average daily dose (mg), study drug compliance, and duration (days) of exposure during the study treatment period.

The duration of study treatment (i.e., drug exposure) is defined as the number of days exposed to treatment, starting with the first dose of study drug through the last dose of study drug

- Duration of study treatment = (last dose – first dose + 1).

If all dispensed kits and bottles are returned, the total number of doses received will be calculated as follows:

- Number of doses received = Total number of doses dispensed – total number of doses returned.

If a dispensed kit or bottle is not returned, the total number of doses received will be calculated as follows:

- Number of doses received = total number of doses dispensed – total number of doses returned – total number of missed doses
- Study drug compliance (%) = $100 \times \text{total number of doses received} / \text{total number of doses expected in each treatment period}$.

Adult patients are expected to receive one dose daily, therefore 84 doses are expected at Week 12.

All study drug dispensation and accountability data will be listed.

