# 10.2. Study Drug Packaging and Labeling

The study drug will be supplied in tamper-evident kits containing two high-density polyethylene (HDPE) bottles. Each bottle will utilize foil induction-seal liners and a child-resistant closure. Each bottle of study drug will contain 30 capsules of 5 mg or 15 mg strength bardoxolone methyl or the matching placebo capsules. Each bottle will also contain a desiccant insert that must not be ingested. Labeling on each kit bottle will contain at minimum the following information:

- Medication ID number;
- Protocol 402-C-1702;
- Caution Statement: New Drug Limited by Federal Law to Investigational Use.
   Keep out of sight and reach of children;
- Control or lot number;
- Store at 20° 25°C (68° 77°F), short term excursions allowed to 15° 30°C (59° 86°F);
- Reata Pharmaceuticals, Inc., Irving, TX.

A double-panel label will be presented on the treatment kit carton containing this and other information as well.

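### SAP 10.2 miscounts doses received when a kit is unreturned, and does not define expected doses for patients who stop early (descriptive exposure summaries only)

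*SAP*

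**What the plan says.** SAP 10.2 derives doses received from dispensing and return records, in two branches. If everything comes back, the rule is "Number of doses received = Total number of doses dispensed – total number of doses returned". If any kit or bottle is not returned, it becomes "Number of doses received = total number of doses dispensed – total number of doses returned – total number of missed doses". The section neither defines a missed dose nor names a source for it.

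Compliance divides doses received by the "total number of doses expected in each treatment period". The only number attached to that denominator is in the sentence "Adult patients are expected to receive one dose daily, therefore 84 doses are expected at Week 12". Duration of treatment, by contrast, is defined per patient, as last dose date minus first dose date plus one. Average daily dose is listed among the summaries without a formula.

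On supply, Protocol 10.2 puts two bottles in a kit and states: "Each bottle of study drug will contain 30 capsules of 5 mg or 15 mg strength". Protocol 9.10.13 has the patient take one capsule from each bottle daily, so a kit holds 30 doses. Protocol 9.10.14 dispenses a kit at Day 1 and Weeks 2, 4 and 8, and at Week 6 only when baseline ACR exceeds 300 mg/g.

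**The concern.** A 30-dose kit that covers 14 or 28 days always has capsules left over, even with perfect adherence. When the kit is returned, the return count removes them. When it is lost, only the missed-dose term could remove them, and a capsule that was never due is not a missed dose in ordinary usage. The formula then credits it as taken.

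The second branch also subtracts the total of missed doses. A dose missed from a kit that was returned is already in the return count, so it comes off twice.

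Total mg, average daily dose and compliance are pre-specified summaries in a titration study whose dosing objective is the highest tolerated dose. With about 25 patients per cohort, a few lost kits or early stops could visibly shift these figures.

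**Working it through.** **Inputs and assumptions.** 30 doses per kit (Protocol 10.2 and 9.10.13); dispensing visits from Protocol 9.10.14; doses by visit from Protocol 7.3.1, Table 4; nominal visit days. Average daily dose is taken as total mg divided by days of treatment, because the SAP gives no formula.

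**The plan's own figure.** 1 dose × 7 days × 12 weeks = 84. It reproduces exactly.

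**True exposure of an adherent completer.**
- ACR ≤300, four kits covering 14, 14, 28 and 28 days: 5×14 + 10×14 + 20×56 = 1330 mg; 1330/84 = 15.83 mg/day.
- ACR >300, five kits covering 14, 14, 14, 14 and 28 days: 5×14 + 10×14 + 20×14 + 30×42 = 1750 mg; 1750/84 = 20.83 mg/day.

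**One kit lost, no dose missed.** Surplus = 30 − days covered. Doses by the formula = 84 + surplus. Added mg = surplus × dose.

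| Baseline ACR | Lost kit | Dose (mg) | Surplus doses | Compliance | Total mg | mg/day | Rise |
|---|---|---|---|---|---|---|---|
| ≤300 | Day 1 | 5 | 16 | 119.0% | 1410 | 16.79 | 6.0% |
| ≤300 | Week 2 | 10 | 16 | 119.0% | 1490 | 17.74 | 12.0% |
| ≤300 | Week 4 or Week 8 | 20 | 2 | 102.4% | 1370 | 16.31 | 3.0% |
| >300 | Day 1 | 5 | 16 | 119.0% | 1830 | 21.79 | 4.6% |
| >300 | Week 2 | 10 | 16 | 119.0% | 1910 | 22.74 | 9.1% |
| >300 | Week 4 | 20 | 16 | 119.0% | 2070 | 24.64 | 18.3% |
| >300 | Week 6 | 30 | 16 | 119.0% | 2230 | 26.55 | 27.4% |
| >300 | Week 8 | 30 | 2 | 102.4% | 1810 | 21.55 | 3.4% |

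If all kits are lost, the formula gives 120/84 = 142.9% (four kits) or 150/84 = 178.6% (five kits).

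**One 14-day kit lost, 7 of its doses missed.** The kit is credited 30 − 7 = 23 doses against 7 taken. Overall this is (70 + 23)/84 = 110.7%, against a true 77/84 = 91.7%.

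**Double subtraction.** An ACR >300 completer misses 10 doses from the first four kits, returns those kits, takes all 28 doses of the Week 8 kit and loses it.
- Returned: 120 − (56 − 10) = 74. True doses: 46 + 28 = 74.
- Formula: 150 − 74 − 10 = 66. Compliance reads 66/84 = 78.6%, against a true 74/84 = 88.1%.

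**Early stop with all kits returned.** An adherent patient stopping at Day 28 has 28 doses. Over own treatment days this is 28/28 = 100%; over 84 it would be 33.3%. Stops at Days 14, 42 and 56 would read 16.7%, 50.0% and 66.7% over 84.

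**The case against.** **The formula does subtract missed doses.** A reader might infer that every unreturned kit is counted as fully taken. The text does not support that: with 7 missed doses, the kit above is credited 23, not 30. One can go further and read missed as every capsule not taken, which removes the surplus error. The SAP does not say this, and the reading works only if the term is confined to unreturned kits. Applied as a total, it would subtract the returned capsules again. For an adherent ACR >300 completer who loses the Week 6 kit, 66 capsule pairs are untaken and 50 are returned, so the line gives 150 − 50 − 66 = 34 doses instead of 84.

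**The SAP does not impose 84 on early stoppers.** It ties 84 to Week 12 and words the denominator by treatment period. A reader might infer a fixed denominator, but what the text shows is an unstated one. Nor does any stated formula put 84 into average daily dose: an adherent Day 28 stopper has (5×14 + 10×14)/28 = 7.5 mg/day whichever compliance denominator is used. The 84 therefore gives no ground for saying that average daily dose reads low.

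**Larger dose effects in ACR ≤300 patients.** A lost Week 4 kit would add 16 × 20 = 320 mg (320/1330 = 24.1%) if these patients also received a Week 6 kit. Protocol 9.10.14 excludes that kit, which makes the rise 3.0%. The dispensing row of Protocol Table 5 marks Week 6 without the limit, and the two places need to be reconciled.

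**Consequences are limited.** This stands. The primary MMRM (SAP 11.1) does not use compliance. The Week 16 off-treatment set (SAP 8.3) is defined by still taking drug at Week 12 and having a Week 16 assessment, not by this percentage. Capsule returns are recorded per bottle (Protocol 10.5) and accountability data are listed, so a figure of 119% could be traced. A figure of 78.6% looks plausible and would be less likely to prompt a check.

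**Conclusion.** The second branch of the SAP 10.2 formula gives wrong counts if followed, and should be corrected. Severity is low, since only descriptive exposure summaries are affected.

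- **Upward error.** If missed means a scheduled dose not taken, each lost kit adds 16 or 2 doses. A single lost kit takes an adherent completer to 119.0% or 102.4%. It raises average daily dose by 3.0% to 12.0% (ACR ≤300) or 3.4% to 27.4% (ACR >300).
- **Downward error.** Missed doses from returned kits are subtracted twice whenever another kit or bottle is lost. The net result depends on the mix; in the example it is 66 doses instead of 74.
- **Gap.** The denominator for early stoppers is not stated. Using 84 would mix persistence with compliance, but the SAP does not say that it will be used.

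The dose figures rest on nominal visit days, on no Week 6 kit for ACR ≤300, and on average daily dose being total mg over duration. How many kits will go unreturned cannot be known from the documents, so the effect on cohort means is not estimated here.

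**What to change.** Revise SAP 10.2 as follows.

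1. Compute doses received kit by kit and sum them. For a returned kit, use dispensed minus returned. For an unreturned kit, use the days from its dispensing to the next kit (or to the last dose), minus the missed doses reported for that kit, capped at 30.
2. Define a missed dose as a scheduled daily dose not taken, and name the data source.
3. Set expected doses to last dose date minus first dose date plus one, which matches the section's own duration rule. If a figure over 84 is wanted, report it separately as the share of planned treatment completed. Whether to remove directed interruption days from the denominator is the sponsor's choice, and the table should say which was done.
4. State the average daily dose formula.
5. Reconcile Protocol 9.10.14 with the Week 6 dispensing mark in Table 5, since kit intervals depend on it.

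With item 1, the adherent completer who loses a 14-day kit returns to 70 + 14 = 84 doses (100%), and the double-subtraction example to 46 + 28 = 74 (88.1%). With item 3, the Day 28 stopper reads 28/28 = 100%.

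The cost is a few lines of SAP text and a minor programming change. It requires missed doses to be attributable to a kit or date; if the case report form does not capture that, a source must be named.

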11. EFFICACY ANALYSES

11.1. Primary Efficacy Analysis

A mixed-model for repeated measures (MMRM) will be used to analyze the primary efficacy variable. The MMRM results will be reported by rare CKD cohort. The ITT population will be used for analysis of the primary efficacy objective. All eGFR values collected closest to the target study day (Section 7.3) through the Week 12 visit will contribute to the primary analysis. The primary efficacy variable, the change from baseline in eGFR value, will be calculated for each first post- first dose time point through Week 12 visit (i.e., Weeks 1, 2, 4, 6, 8, and 12). Missing data will not be imputed for the primary analysis. The primary inference will be the test of LS mean at each time point. The primary endpoint is the mean change from baseline in eGFR at Week 12.

The eGFR values collected after the study window of study drug discontinuation will be not be used in primary or exploratory efficacy analyses.

11.1.1. Statistical Hypothesis

For the primary efficacy objective, the null hypothesis is the Week 12 mean (μ_{BARD}) change from baseline in eGFR = 0 mL/min/1.73 m². The alternative hypothesis is the Week 12 mean (μ_{BARD}) change from baseline in eGFR \neq 0 mL/min/1.73 m².

11.1.2. Statistical Model

The MMRM model will include the change from baseline in eGFR value as the dependent variable, protocol scheduled time point (analysis visit) as a fixed effect, patient as a random effect, and the baseline eGFR and log-transformed baseline ACR as continuous covariates. Within-patient correlations will be modeled using an unstructured covariance structure. Time ordering is a repeated measure within patients. It is assumed that errors for different patients are independent with an unstructured covariance structure. The estimation method for the model will be restricted maximum likelihood (REML). The SAS pseudo-code is as follows:

```
proc mixed data=efficacy method=reml;  
  class usubjid avisitn;  
  model chg=avisitn base_egfr lbase_acr;  
  repeated avisitn / subject=usubjid type=un rcorr;  
  lsmeans avisitn / diff cl alpha=0.05;  
run;
```

In the event the MMRM model with an unstructured covariance structure does not converge, the following covariance structures will be as substitution in the following order. Each subsequent covariance structure will be used only if all previous covariance structure(s) is (are) used and the model(s) did not converge.

1. Toeplitz covariance structure (assuming measurements from samples taken closer together in time are more highly correlated than those from samples taken farther apart).
2. First order of auto-regressive [AR(1)] covariance structure (assuming measurements from samples taken closer together in time are more highly correlated than those from samples taken farther apart).
3. Compound symmetry covariance structure (assuming equal correlation for measurements from a patient, regardless of how far apart in time when they were taken).

A separate MMRM model will be analyzed for each rare CKD cohort.

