#### 7.2. Number of Patients

Each cohort will enroll approximately 25 patients, for a total of approximately 100 patients in the trial.

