## 7.4. Criteria for Study Termination

Although the Sponsor intends to complete the study, the Sponsor reserves the right to discontinue a cohort or the study at any time for clinical or administrative reasons, or if required by regulatory agencies. If the Sponsor discontinues the study, all study drug will be discontinued and the investigator will be responsible for securing any alternative therapy to be administered, as appropriate.

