11.1.3. Reporting Results

The least squares (LS) mean, standard error (SE) of the LS mean, two-sided 95% confidence interval (CI) of the LS mean and p-value will be reported at each time point. Statistical testing will be performed at every time point that eGFR is measured. The change from baseline in

eGFR at Week 12 is the primary endpoint. A formal test of mean change from baseline in eGFR $\neq 0$ will be conducted at Week 12. The mean change from baseline in eGFR at all other time points will be considered exploratory, so tests at these time points will be performed with no adjustments for multiple comparisons.

A plot of the LS means with 95% CIs of change from baseline in eGFR value over time will be presented.

Descriptive statistics for observed eGFR values and change from baseline in eGFR values will be provided by time point through the end of follow-up. A plot of mean and standard error of eGFR values over time will be presented.

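### Minor: the primary Week 12 test names no small-sample degrees-of-freedom method, and its fallback covariance structures put one common variance on all visits

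*SAP*

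**What the plan says.** SAP 11.1.2 gives PROC MIXED pseudo-code for a REML fit in each cohort, with visit and two baseline covariates in the MODEL statement and "repeated avisitn / subject=usubjid type=un rcorr" for the covariance. The code has no ddfm option, no RANDOM statement and no empirical standard error. The accompanying text nevertheless lists "patient as a random effect, and the baseline eGFR and log-transformed baseline ACR as continuous covariates".

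The fallback rule reads: "In the event the MMRM model with an unstructured covariance structure does not converge, the following covariance structures will be as substitution". Toeplitz comes first, then AR(1), and last "Compound symmetry covariance structure (assuming equal correlation for measurements from a patient". The notes beside the three names describe how correlation behaves over time. They say nothing about variance, and none of the three is called heterogeneous.

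SAP 11.1.3 makes Week 12 the only formal test: it "will be conducted at Week 12. The mean change from baseline in eGFR at all other time points will be considered exploratory". On missing data, SAP 11.1 states: "The eGFR values collected after the study window of study drug discontinuation will be not be used in primary or exploratory efficacy analyses". On size, Protocol 7.2 states: "Each cohort will enroll approximately 25 patients, for a total of approximately 100 patients in the trial". SAP 12.7.1 reuses the 11.1.2 model for Week 16, and SAP 12.7.2 repeats the fallback list.

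**The concern.** The one formal test in each cohort rests on the Week 12 standard error and its reference distribution. Two features of that test are left open or weakened.

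(a) An unstructured matrix over six visits is estimated from about 25 patients, and values after drug discontinuation are removed. When data are missing, the Week 12 estimate borrows from earlier visits through estimated covariances. An unadjusted standard error ignores the uncertainty in those covariances. This applies at the planned size.

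(b) The unstructured model gives Week 12 its own variance. All three fallbacks give that up, so the Week 12 standard error becomes an average over visits. Whether this helps or harms depends on how the spread of eGFR change evolves over the 12 weeks, which the documents do not say.

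**Working it through.** **Inputs from the documents.** Two-sided 5% level (SAP 7); about 25 patients per cohort (Protocol 7.2); post-baseline visits at Weeks 1, 2, 4, 6, 8 and 12 (SAP 11.1); two continuous covariates (SAP 11.1.2).

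**Assumed, because not given.** Visit SDs, within-patient correlation, dropout, and the degrees of freedom (df).

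**The plan's own figure.** SAP 6 states about 80% power at 25 patients. A two-sided one-sample t test reaches 80% at n = 25 for a standardised change of 0.584. The effect and SD behind the statement are redacted, so it can be neither confirmed nor refuted. Nothing below depends on it.

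**Parameter count.** Unstructured over six visits: 6 × 7 / 2 = 21 covariance parameters.

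**(a) Degrees of freedom.** Unstructured REML fits were simulated at n = 25 under a true null. The unadjusted test used 25 - 3 = 22 df. The ranges span two separately written REML programs.

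| Assumed dropout | Unadjusted, n-3 df | Kenward-Roger |
|---|---|---|
| 20% | 5.6-6.1% | 4.6-5.2% |
| 35% | 7.0-7.3% | 5.5-5.7% |

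With complete data the two methods do not differ. For scale, a 5% rate from 1,000 to 2,500 runs has a Monte Carlo SE of √(0.05 × 0.95 / runs), about 0.7 to 0.4 points.

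**(b) Pooled standard error given fallback.** With one common variance, model SE / true SE at Week 12 is k = √(mean visit variance / Week 12 variance). Type I error is 2 × [1 - Φ(t_crit × k)]. Two df choices were used: within-subject, 150 records - 25 - 5 = 120 (t_crit 1.980), and n-3 = 22 (t_crit 2.074). The SD rises linearly from Week 1 to a plateau at Week 4, 6 or 12.

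Example, SD ratio 1.5 with plateau at Week 6:
- SDs are 1, 1.1, 1.3, 1.5, 1.5, 1.5.
- Mean variance is (1 + 1.21 + 1.69 + 3 × 2.25) / 6 = 1.775.
- k = √(1.775 / 2.25) = 0.888.
- 1.980 × 0.888 = 1.76 gives 7.9%; 2.074 × 0.888 = 1.84 gives 6.5%.

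Type I error for plateau at Week 4 / Week 6 / Week 12:

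| Week 12/Week 1 SD ratio | 120 df | 22 df |
|---|---|---|
| 0.67 | 2.2 / 1.8 / 1.0% | 1.7 / 1.3 / 0.7% |
| 1 | 4.8% | 3.8% |
| 1.25 | 6.1 / 6.6 / 8.0% | 4.9 / 5.4 / 6.7% |
| 1.5 | 6.9 / 7.9 / 10.8% | 5.7 / 6.5 / 9.3% |
| 2 | 8.0 / 9.6 / 15.1% | 6.7 / 8.1 / 13.3% |

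The closed form treats the pooled SE as known, so its reference at ratio 1 is 4.8% or 3.8%, not exactly 5%.

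REML fits of the three listed structures, forced at n = 25 with 20% dropout and ratio 1.5, gave 7.4-7.8 / 8.0-8.4 / 10.8-11.2%. With 22 df on both sides at that ratio, the listed structures gave 6.1-10.4% and the heterogeneous versions 3.0-4.8%.

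The distortion does not grow as the cohort shrinks. At ratio 1.5, with SD rising in equal steps per visit, k was 0.84-0.85 at n = 25 and 0.82-0.84 at n = 12.

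**How often fallback is reached.** Unstructured fits that failed to converge, in three REML programs (none is PROC MIXED):

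| Patients | Program 1, 20% dropout | Program 2, 10% / 25% dropout, 40 runs each | Program 3 |
|---|---|---|---|
| 25 | 0/2000 (0/1200 at 35%) | 0% / 0% | 1/2500 (20% dropout) |
| 20 | 0/1200 | 0% / 10% | not run |
| 15 | 22/2500 (0.9%) | 15% / 27.5% | 32/600 (5.3%) |
| 12 | 957/6600 (14.5%) | 37.5% / 60% | 177/600 (29.5%) |

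The programs agree that failure is very rare at 25 and a real possibility at about 15 or fewer. The exact rates depend on the optimizer.

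**The case against.** The best defence is that (b) concerns a contingency the plan is not expected to meet. Fallback is all but absent at 25 patients, even with 35% dropout. The route to a much smaller cohort is mainly the general clause in Protocol 7.4 that "the Sponsor reserves the right to discontinue a cohort or the study at any time for clinical or administrative reasons", and nothing says a cohort of about 12 is foreseen. The SD ratios are assumed. At ratio 1.25 with a Week 4 plateau and 22 df, the figure is 4.9%, which is no inflation above the nominal 5%. The largest figures need the SD to rise right up to Week 12. Titration ends at Week 4 or 6 (Protocol 7.3.1) and the Protocol's introduction places early eGFR gains in the first four weeks, so a plateau is at least as plausible. Heterogeneous structures can also fail: among 979 simulated fallback cases with 12 to 15 patients, heterogeneous Toeplitz could be fitted in 636, ARH(1) in 342 of the rest and CSH in the last one. Nor do they fully restore 5%: in simulated cohorts of 12 that reached fallback at ratio 1.5, they rejected 45 of 611 times (7.4%).

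All of that stands, and it keeps (b) minor. It does not touch (a), which arises at the planned size and needs no fallback. One can answer (a) by saying that pseudo-code need not show every option. But no df method is named anywhere in the readable text for the primary model, so the choice remains open.

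Three stronger readings are tempting and are not supported:

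- A reader might infer that the fallback list inflates the false-positive rate of the trial as planned. It does not at about 25 patients, and the direction of any error is unknown without visit SDs.
- A reader might infer that smaller cohorts suffer a larger distortion. Size governs whether fallback is triggered, not how large the error then is.
- A reader might infer that a random patient effect on top of an unstructured matrix (22 parameters, rank 21) makes the primary model unidentifiable and so forces fallback at any size. That holds only for the text read literally. The pseudo-code has no RANDOM statement, so it does not arise if the code is followed.

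**Conclusion.** Both points hold and both are minor.

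(a) At the planned size the unadjusted Week 12 test is slightly anti-conservative when data are missing: by about half a point to one point at 20% dropout and about two points at 35%. Kenward-Roger brings it to within about 0.7 points of 5%. This rests on assumed dropout, correlation and n-3 df.

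(b) Given fallback, the Week 12 standard error is pooled. At an assumed SD ratio of 1.5 the type I error is about 6-11%, depending on SD shape and df. It is conservative if the SD falls over time and has no such error if variances are equal. For cohorts of about 25 this is close to inert.

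The point carries into SAP 12.7.1, which reuses the model with Week 16 added; that model was not simulated. It is weaker for SAP 12.7.2: ACR is collected at only four post-baseline visits (Weeks 4, 8, 12 and 16 in SAP Table 2), so that model has at most 4 × 5 / 2 = 10 covariance parameters.

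**What to change.** 1. In SAP 11.1.2, add ddfm=kr to the MODEL statement and name the method in the text. This also covers 12.7.1. It is one option, with no protocol amendment, and makes no difference to the Week 12 test when data are complete.
2. In the 11.1.2 fallback list, put heterogeneous Toeplitz (TOEPH), ARH(1) and CSH ahead of the present Toeplitz, AR(1) and compound symmetry, which stay as the last resort. This takes a few lines of SAP text. Each heterogeneous structure has five more variance parameters. Intervals are about 9-10% wider only when fallback is used and variances are in fact equal.
3. Optional: make the same change to the list in 12.7.2.
4. Optional clean-up: remove the random patient effect from the SAP model text so that it matches the code. The same wording stands in Protocol 12.3.1, so an SAP-only edit leaves a mismatch there. Protocol 12.3 gives the SAP precedence on analysis, so no amendment is needed for that alone.
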